12.1 STUDY INFORMATION

12.1.1 Protocol

Study No.: WLI-4306-HAV

Clinical Investigation – Havana, Cuba

1. **Title:** SeraSeal, A Primary hemostatic Agent, Clinical Study
2. **Principal Investigator:** [name] [name]
[name] [name]
[name] [name]
[name] [name]
[name] [name]
[name] [name]
[name] [name]
[name] [name]
[name] [name]
[name] [name]
3. **Monitors:** [name] [name]
[name] [name]
[name] [name]
4. **Identification of the Research:** This study focuses on treatment of bleeding wounds
4. **Location:** Joaquin Albarran Hospital, Havana, Cuba
Salvador Allende Hospital, Havana, Cuba
National Institute for Cardio-Vascular Surgery, Havana, Cuba

5. Research Plan:

5.1 Purpose: SeraSeal was designed as a primary hemostatic agent to control all forms of bleeding. In this study, SeraSeal is to be applied from the initial incision, and throughout the entire surgical procedure to closing without any intervention of standard surgical methods to control bleeding. Only one delivery system, syringe or spray of SeraSeal is to be used for that particular surgical case without any cross-over.

5.2 Hypothesis or Research Questions or Objectives: The null hypothesis is that SeraSeal will not be more effective than surgical modalities to control bleeding in surgical cases historically known to take more than 6 minutes to control all of the hemorrhages. The alternative hypothesis is that SeraSeal will have a collective time to hemostasis of less than 5 minutes in 95% of the surgical cases.

5.3 Significance: SeraSeal shows promise of being a superior hemostatic agent applicable to wounds, surgical operations in which hemostasis is difficult (hepatic, renal and splenic trauma, debridement, burns, skin grafting, endoscopic procedures), control of epistaxis, esophageal variceal bleeding, bleeding peptic ulcers, and bleeding associated with proctitis and cystitis. For some of these conditions, there is no entirely satisfactory treatment.

5.4 Relevance: The availability of an easy to use, stable, safe, effective hemostatic agent, would be a tremendous advantage to the trauma patient (surgical or accidental), possibly reducing morbidity and mortality significantly, and conserving surgical and blood resources.

5.5 Background and Review of Literature:

Problem with Bleeding Wounds

Bleeding is still a major cause of morbidity and mortality in wounds. Thirteen percent of patients suffering acute trauma, die of bleeding¹⁻¹¹. Of the total deaths occurring on the battlefield, eight-five percent are due to blood loss¹². Particularly vulnerable areas are the face, groin, pelvis and extremities, areas not protected by body armor. In head and neck trauma, uncontrolled bleeding can cause airway compromise and asphyxiation¹³. In trauma survivors, inability to control bleeding leads to blood transfusion, increased complication rates, immunosuppression, inability to generate red blood cells, and prolonged time in the hospital. The ideal solution to these problems is to control the bleeding in the first place. The limiting factor in performing burn debridement of chronic wounds results in bleeding, which is essentially an end point for debridement, because there is no satisfactory way of controlling bleeding in granulation tissue. This results in repeated debridement. Bleeding is a major cause of skin graft loss and flap necrosis. Outside of the hospital, the paramedic has only compresses to control bleeding. A quick, effective, and safe device to control bleeding, would be extremely beneficial.

Hemostatic agents in wounds

Commercially available topical thrombogenic agents include microfibrillar collagen (Avitene®), collagen sponges (Gelfoam®, Instat®), and fibrin sealants (Tisseel®, AFTA®, ViGuard®). Topical collagen preparations have been available for more than 25 years and have a limited ability to facilitate clotting. When hemorrhage is excessive or the patient's clotting factors are inhibited, they are less effective.

Fibrin Sealants

These are prepared from homologous, pooled human or bovine fibrinogen, Factor XII, and thrombin that must be combined to make the fibrin. Other components include calcium to provide activation of Factor XIII, fibronectin to aid in adhesion, and an inhibitor of fibrinolysis to prolong fibrin clot life. Fibrin sealants have shown great promise in controlling wound hemorrhage. Fibrin sealants have been shown to reduce operating time, blood loss, and do not appear to interfere with healing¹⁴. When applied to a ballistic wound as a dry dressing, the sealant reduced blood loss by 64%¹⁵.

Problems with current tissue sealants

Several problems exist with the commercially available fibrin sealants: They are a two part system of fibrin and thrombin, which must be mixed at operation or trauma setting, adding to the operative time and delaying transportation to a stable operative setting. Previously, the FDA withheld approval from European products because they used pooled human plasma as a product source¹⁶. The fibrin sealants are somewhat difficult to use, as they must be mixed from four components, a process which takes approximately 15 minutes, and then must be used within four hours. If they are to be used endoscopically, they must be placed through a dual lumen catheter and mixed in situ¹⁷. Their viscosity makes application difficult via catheters and in small areas, and limits methods of application such as sprays, or foams, which would be useful for large wounds. The time between mixing and hemostasis can be several minutes, typically 3-5 minutes, further slowing operation repair¹⁸. The incorporation of fibrin sealants into a dry dressing has reduced some of these problems. The strength of the clot formation, when utilizing a dry dressing, can be sub-optimal. These shortcomings limit the utility of fibrin sealants for hemostasis in the battlefield, emergency response teams such as paramedics, and in the surgical arena.

Bovine topical thrombin in most cases, is a heterologous plasma thrombin concentrate that has been used for hemostasis since the 1940's. Some commercial bovine thrombin preparations are highly immunogenic, and appear to be associated with an increased risk for adverse clinical outcomes during subsequent surgical procedures¹⁹. Antibody formation and anaphylaxis (rates 0.5 to 5.8%) have also been seen with Factor V and aprotinin, a polyvalent proteinase inhibitor isolated from bovine lungs, and used alone to enhance clot stability, or in combination with fibrin sealants^{20,21}. These antibodies may interfere with the heparin anti-Xa assay,

thereby complicating the monitoring of anticoagulant therapy²². The commercially available product, Tisseel VH fibrin sealant, contains bovine aprotinin, resulting in the risk of hypersensitivity²³.

What this study will determine

This study is designed to determine whether SeraSeal is effective as a primary hemostatic agent, and safe in achieving hemostasis in surgical wounds or other emergent hemorrhagic episodes. The effectiveness will be determined by achieving hemostasis after application of the product. The safety will be determined by monitoring outcomes from application: recurrence of bleeding, infection, lack of healing, and presence of hypersensitivity reactions, e.g. pruritus, fever, rash, anaphylaxis.

Characteristics of SeraSeal

SeraSeal is a bovine protein-derived accelerator of hemostasis interacting with the intrinsic and extrinsic pathways. It is obtained from pathogen and prion free cows. SeraSeal can be provided as a solution, spray, foam, incorporated into an absorbable dressing or a non-absorbable removable dressing. Its active ingredients are Factors IIa, VIIa, IXa, and Xa.

Toxicity of SeraSeal

A total dosage level of SeraSeal over 13,000 IU/Kg (2.4 mg protein) in leporids and canines had no adverse effects^{24,25}. The total expected treatment levels to be used in this study is less than 1,000 IU/Kg, a thirteen fold lower level than the no toxic effect. Thus, drug related toxicity is not expected to be seen in this clinical study. Cell culture studies reveal that SeraSeal is not directly toxic for any cells tested.

5.6 Research Design and Methods: This clinical trial will be a non-randomized, unblinded study where SeraSeal will be used as a liquid, administered by a syringe (300 IU/0.1ml) or spray (210 IU/pump), and compared to standard surgical methods to control bleeding in historically known surgical cases taking more than 6 minutes to control all of the hemorrhages. The intent-to-treat patients will be placed into either the SeraSeal syringe treatment group, where bleeding from medium to large blood vessels may occur, or the SeraSeal spray treatment group, where only capillary to small blood vessels would be treated with the investigational product.

Patients receiving treatment at Joaquin Albarran Hospital, Salvador Allende Hospital, and National Institute for Cardio-Vascular Surgery, will serve as study volunteers. Prior to enrollment in the study, an initial screening test and subsequent studies will take place, including: informed consent, collection and recording of subject demographic information, medical history, current medications, assessment of inclusion/exclusion criteria, physical examination, with blood draws for hematological assessment for bleeding and time to hemostasis. The location of the study wounds will be skin-skin. The study wound sites will involve bone and soft tissue.

The primary endpoint in this clinical trial is hemostasis. A Secondary endpoint is the number of surgical cases without a therapeutic break from SeraSeal to a standard surgical modality to control the bleeding. There are 10 designated surgical faculty members from General Surgery, Vascular, Obstetrics and Gynecology participating in this study, with a minimum of 10 surgical procedures being studied. All of the participating surgeons are highly skilled and have extensive expertise in their surgical specialty.

In this trial, the dosage level of SeraSeal vial is 300 IU/0.1ml and 210 IU/pump in the spray, with a maximum expected dosage of 10,000 IU, 20 times less than the pre-clinical toxicity studies. After 1-2 minutes, when hemostasis is achieved, the excess SeraSeal will either be removed through suction or absorption onto a surgical sponge. A time to hemostasis is measured from the time when the product is first applied to the wound, until no bleeding or oozing is observed from the wound. A nurse will use a stopwatch to record the time to hemostasis. SeraSeal will be used from the initial incision and through out the entire surgical procedure, and the time to hemostasis for each bleed will be measured, then totaled for the entire surgery. SeraSeal is expected to achieve a total hemostasis time under 5 minutes. Stopping criteria for treatment will be when hemostasis fails to be achieved after 3 applications for a particular wound, the collective time to hemostasis exceeds 5 minutes, the patient experiences a serious adverse event, or at the surgeons discretion. If this should happen, the patient will be switched over to standard surgical practices.

The patients will be monitored for post-operative bleeding and overall wound healing for those wounds that can be observed. A base line hemoglobin (HGB), hematocrit (HCT), prothrombin time (PT), partial thromboplastin time (PTT) be drawn, and measured at 24 to 48 hours after surgery. The patients will be observed and assessed for a minimum of 48 hours after application of SeraSeal for signs of post-operative bleeding, and hypersensitivity to the investigational product throughout the hospitalization period. They will be assessed for, but not limited to, skin rash; wheezing; anaphylaxis; pruritus; prolong coagulation tests; delayed healing or infection through quantitative cultures. In the event there is progression of edema leading to respiratory distress, anaphylaxis, or shock due to blood loss, a crash cart and/or any additional standard and customary treatment(s), will be available. This study will not limit the standard of care performed at the four investigational hospitals. The following components of wound care are "standard practice" at each of the hospitals: daily dressing changes; quantitative cultures when infection may be present; routine blood tests. All enrolled study subjects may request to be withdrawn from the study at any time, and will be terminated from the study and provided standard of care. All adverse events will be recorded according to whether the event was unrelated, unlikely, possibly or probably related to the study treatment.

Table 1: Schedule of Assessments

Test	Pre-Op	Surgery	4-8 Hrs Post-Op	24-48 Hrs Post-Op
Informed Consent	X			
History		X		
Physical Examination	X		X	X
HGB	X		X ⁺	X [#]
HCT	X		X ⁺	X [#]
PT	X		X ⁺	X [#]
PTT	X		X ⁺	X [#]
ECG	X		X ⁺	X [#]
Radiological work-up	X		X ⁺	X [#]
Adverse Events		X	X	X [#]
Effectiveness		X	X	X
Safety		X	X	X

+ measured as often as needed.

monitored beyond 48 hours and as needed

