6.3 Safeguards for Protecting Subjects: The risks of SeraSeal treatment are minimized by the patient selection process. Should an allergic reaction occur, the participant will be withdrawn from the study and standard of care administered. Physicians, nurses, and technicians, will be on hand for all procedures. Patients will be monitored through routine post-operative care. Should any adverse event occur during treatment, immediate intervention is possible. A crash cart is kept in the treatment room and on the hospital floor. Patient records will be kept confidential.

6.4 Alternatives: Alternatives to SeraSeal are the application of no hemostatic agents, electric cauterization, ligature, pressure dressings, collagen dressings, and the use of fibrin sealants. The application of other dressings containing proteins, carries the risk of allergic reaction.

7.0 Data Analysis:

7.1 Data Collection: There will be one study form for each patient. The surgery form will have all of the outcome data and adverse events. Once the patient's surgical procedure qualifies for the study, the patient will be asked to participate in the clinical trial by the participating investigator surgeon. The only patients that will require special action are the SeraSeal patients. For those patients the need for SeraSeal will be made known only to the attending surgeon and/or fellows, and made available to the OR room. At the time of the pre-op exam, the inclusion/exclusion of participation in the study will be filled out. The monitor board member will collect all data forms and will be responsible for evaluating them for completeness and accuracy, except for time to hemostasis supplied by the surgeon.

7.2 Statistical Analysis: We will compare continuous outcomes such as time to hemostasis (primary outcome), and therapeutic breaks from SeraSeal to standard surgical modalities to control bleeding. This study will use a relatively simple method of analyzing the data generated by employing a non-parametric statistical analysis,

using the chi-square distribution.

For continuous lab outcomes measured on two occasions (base, 24- 48 hours), we will use repeated measure analysis of variance methods to compare mean lab values for conventional versus SeraSeal® overall.

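### The null and alternative hypotheses concern different quantities, and the method named for the primary outcome gives no reference rate or success rule for the claim of 95% of cases under 5 minutes

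*Protocol*

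**What the plan says.** Protocol section 5.2 states the null as a comparison: "The null hypothesis is that SeraSeal will not be more effective than surgical modalities to control bleeding". It confines this to operations whose bleeding, by past experience, needed longer than 6 minutes to bring under control. The other hypothesis in that section is a proportion in one group: "The alternative hypothesis is that SeraSeal will have a collective time to hemostasis of less than 5 minutes in 95% of the surgical cases".

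Section 5.6 describes a non-randomized, unblinded study with standard surgical methods as the historical reference. Both groups receive the product: "The intent-to-treat patients will be placed into either the SeraSeal syringe treatment group" or the spray group. The section says "The primary endpoint in this clinical trial is hemostasis", then defines time to hemostasis for each bleed and totals it over the operation. A case whose total passes 5 minutes is switched to standard practice.

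Section 7.2 says of the analysis: "We will compare continuous outcomes such as time to hemostasis (primary outcome), and therapeutic breaks from SeraSeal to standard surgical modalities to control bleeding". The method is a non-parametric analysis "using the chi-square distribution". No statistic, reference value or criterion for success follows. The sample-size paragraph names total time to hemostasis as the primary outcome and gives 95% within 5 minutes as the expected result. It bases 120 patients on a 95% confidence level, a confidence interval of 5 and 175 surgical cases per day.

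**The concern.** A null and an alternative should divide the possible values of one parameter between them. Here the null concerns a difference from other methods and the alternative concerns a single rate. A result can refute the first without bearing on the second, and some true states satisfy neither.

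The analysis section does not close the gap. It promises a comparison of a continuous outcome, and nowhere says how the observed share of cases under 5 minutes will be judged against 95% or any other value. The stake is the trial's main efficacy claim: the null could be rejected and the 95% statement then reported as established without having been tested. The same data could also count as success or failure, depending on which reading of 95% is adopted after the results are known.

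**Working it through.** **Do the hypotheses fit together?** Let p be the proportion of cases with collective time under 5 minutes. Suppose p = 0.90 and SeraSeal is faster than historical practice. The null is false, because SeraSeal is more effective. The alternative is also false, because 90% is not 95%. The two statements are therefore not complements.

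**Does the sample size imply a test of 95%?** The stated size can be reproduced as a survey precision calculation: n0 = z²p(1−p)/d², then n = n0/(1+(n0−1)/N), with z = 1.96, d = 0.05 and N = 175.

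- With p = 0.5 (not stated in the protocol): n0 = 384.1, n = 384.1/(1 + 383.1/175) = 120.4. This matches 120.
- With the protocol's own 0.95: n0 = 73.0, n = 73.0/(1 + 72.0/175) = 51.7. This does not.

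So 120 comes from a precision formula into which the 95% does not enter. It supplies no null rate, test or power.

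**What would 120 patients show about 95%?** X is the number of cases under 5 minutes, binomial with n = 120. The true rates other than 95% are assumptions.

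*Reading A: 95% must be exceeded.* For H0: p ≤ 0.95 at one-sided 0.025, find the smallest r with P(X ≥ r | 0.95) ≤ 0.025.

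- P(X ≥ 118 | 0.95) = 0.058, too large.
- P(X ≥ 119 | 0.95) = 0.95¹²⁰ + 120 × 0.95¹¹⁹ × 0.05 = 0.0021 + 0.0134 = 0.0155, so r = 119.
- P(X ≥ 119) is 0.305 at p = 0.98 and 0.662 at p = 0.99.

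The exact (Clopper-Pearson) two-sided 95% lower limits agree: 95.4% for 119/120 and 94.1% for 118/120.

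*Reading B: an observed 95% is enough.* 0.95 × 120 = 114. P(X ≥ 114) is 0.606 at p = 0.95, 0.147 at 0.92 and 0.038 at 0.90. The exact 95% confidence interval for 114/120 is 89.4% to 98.1%.

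*Reading C: 95% is the expected rate, tested against a lower null rate p0.* The documents give no p0. Over an assumed range, with a one-sided exact test at 0.025:

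| p0 | Successes needed | Actual alpha | Power at a true 95% |
|---|---|---|---|
| 0.85 | 110 | 0.022 | 96% |
| 0.87 | 112 | 0.020 | 85% |
| 0.88 | 113 | 0.019 | 75% |
| 0.90 | 115 | 0.016 | 44% |

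The bar thus runs from 110 to 119 successes across readings that the protocol leaves open.

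**The case against.** The best defence is that section 7.2 is loose rather than wrong: a one-sample chi-square test of observed against expected counts (114 and 6) could be built from its words. That is possible, so one cannot say that the text rules out every test of 95%. But the protocol describes a comparison and names no expected count. Such a test would also make 95% the null value, the reverse of section 5.2. For example, 110/120 gives (110−114)²/114 + (10−6)²/6 = 2.81, p = 0.094, and failing to reject there would not demonstrate 95%.

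A second defence is that the sample-size paragraph sets an estimation framework, and the interval for 114/120 is indeed roughly 5 points either side. This stands as far as it goes, but a confidence level for an estimate is not an error rate for a decision, and section 5.2 poses hypotheses. Test details may sit in an unseen SAP, but the mismatch between the hypotheses is in the protocol itself.

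Four stronger readings are tempting and are not supported:

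- That chi-square is the only method in the plan. Section 7.2 also names repeated measures analysis of variance, for laboratory values. Chi-square is the only method named for the primary outcome.
- That syringe and spray results will be pooled for the primary outcome. The word overall is attached to laboratory and binary outcomes, not to time to hemostasis.
- That there are three competing primary endpoints. Section 5.6 defines hemostasis through its timing, and the sample-size text agrees with 7.2 that total time is primary. What is unsettled is whether that time is analysed as continuous or cut at 5 minutes.
- That a p0 of 85% to 87% is the right one. Those values give adequate power at 120 patients, but nothing in the documents supports them.

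**Conclusion.** The point holds. Sections 5.2 and 7.2 state a null and an alternative about different quantities and provide no reference rate or success rule for the 95% claim. This is wrong as written, not detail left for later, because rejecting the stated null would not establish the stated alternative.

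The size depends on the reading. As a value to be exceeded, 95% is almost out of reach with 120 patients (119 successes needed). As an observed threshold, it would be missed about 39% of the time (1 − 0.606) when the true rate is exactly 95%. As an expected rate, power ranges from 96% to 44% over the assumed p0 values. These figures assume 120 evaluable, independent cases.

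**What to change.** In sections 5.2 and 7.2, name one primary endpoint: the proportion p of treated cases with collective time to hemostasis under 5 minutes. State H0: p ≤ p0 against H1: p > p0, analysed by a one-sided exact binomial test at 0.025 with an exact confidence interval, in place of the chi-square analysis of time to hemostasis. Treat 95% as the expected rate. The sponsor should fix and justify p0 before any data are seen, then check whether 120 patients give adequate power for that value.

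The text changes are short and need no new patient data. The costs are in the claim. The formal conclusion becomes that the rate lies above p0, with 95% as an estimate. Any statement of superiority to standard surgical methods must be dropped or tied to a defined historical data source, and a defensible p0 is likely to need such a source too.

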5.7 Inclusion/Exclusion Criteria

4.1 Inclusive criteria:

1. Patients over the age of 18
2. Patients of both sexes
3. Patients who are on anticoagulant therapy
4. Patients with a history of blood disorders

4.2 Exclusion criteria:

1. Patients who are pregnant
2. Patients suffering from mental disease
3. Patients with the HIV virus
4. Patients with a history of anaphylaxis
5. Patients receiving treatment with beta-blockers
6. Patients with sensitivity to bovine proteins
7. Patients with signs of infection
8. Patients who during surgery show signs of sepsis
9. Patients with sensitivity to iodine.

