5.8 Source of Research Material

5.9 Number of Subjects: A total of 120 subjects, are to participate in this study.

6.0 Recruitment: Subjects will be selected from within each participating surgical department at Joaquin Albarran Hospital, Salvador Allende Hospital, and National Institute for Cardio-Vascular Surgery. The faculty from each hospital will obtain an informed consent, prior to their participation in the study. No promotional fliers are planned. The consent form will be provided by both hospitals in Spanish. Subjects will not be paid for participation in this study.

6.1 Benefits: The possible benefit of the patient's participation in this study is a faster time to clotting, less blood loss, faster wound healing, and less loss of tissue. However, the participant should understand there is no guarantee or promise that they will receive any benefit from this study, other than knowing that the information may help future patients.

6.2 Risks: The risks of application of SeraSeal are theoretical. These risks may be bleeding, infection, and allergic reaction. Anaphylaxis is a possible risk, but the incidence is not clearly known. Aprotinin, a bovine protein derived from the bovine lung, is used in cardiac surgery and is the component of some fibrin sealants. It has an anaphylaxis rate of 2.5% on second exposure, with a mean interval of 1,654 days (range, 16-7,136 days)²⁶. SeraSeal contains no aprotinin. Bovine gelatin is a component of some vaccines and anaphylaxis has been reported with this protein²⁷. Other bovine proteins for which anaphylaxis and hypersensitivity reactions have been reported, are bovine serum albumin²⁸, thrombin^{29,30}, recombinant Factor VIII³¹, insulin³², and tissue sealants³³. The risk of anaphylaxis appears to be lower for topical devices than injected ones, and repeated administration with a break, as proposed in this study, also appears to have a lower incidence of anaphylaxis²⁴. We surmise that anaphylaxis may be a risk of application of SeraSeal. Measures to reduce and treat anaphylaxis is to exclude those patients who are sensitive to bovine proteins from the study, and to provide a crash cart, and/or any additional standard and customary treatment(s). One of the purposes of this study is to determine that risk. Reports of an autoimmune reaction to fibrin sealants containing bovine Factor V mimicking hemophilia have been reported. SeraSeal does not contain Factor V.

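### The safety outcomes and named risks of a procoagulant product leave out thromboembolic events and occlusion of a treated vessel

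*Protocol*

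**What the plan says.** Section 5.5 (What this study will determine) states the basis of the safety conclusion: "The safety will be determined by monitoring outcomes from application: recurrence of bleeding, infection, lack of healing, and presence of hypersensitivity reactions". Section 6.2 describes the risks as theoretical and lists them: "These risks may be bleeding, infection, and allergic reaction". The rest of 6.2 deals with allergic and immune reactions.

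Section 5.5 (Characteristics of SeraSeal) calls the product a "bovine protein-derived accelerator of hemostasis interacting with the intrinsic and extrinsic pathways" and adds: "Its active ingredients are Factors IIa, VIIa, IXa, and Xa". Section 5.6 describes the "SeraSeal syringe treatment group, where bleeding from medium to large blood vessels may occur". Vascular surgeons take part, and one site is a cardiovascular surgery institute.

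For post-operative follow-up, section 5.6 says: "They will be assessed for, but not limited to, skin rash; wheezing; anaphylaxis; pruritus; prolong coagulation tests; delayed healing or infection through quantitative cultures". Patients are watched for at least 48 hours for bleeding and hypersensitivity. Adverse events of any kind are recorded with a relatedness grade. Table 1 has columns before, during, 4-8 hours after and 24-48 hours after surgery. Section 8 sets participation at 30 days after the procedure.

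**The concern.** The named outcomes cover too little effect (re-bleeding), wound problems (infection, poor healing) and reactions to a bovine protein. They do not cover too much of the intended effect. For a product that the protocol itself describes as speeding up clotting, an unwanted clot or a blocked vessel is the obvious counterpart to re-bleeding.

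The consequence is one of ascertainment. An event that is neither named nor asked about is counted only if it shows itself and someone thinks to write it down. An analysis plan cannot repair this later, because it cannot recover events that were not looked for. If the trial then concludes that the product is safe on the stated list, that conclusion says nothing definite about clotting. This bears on patient safety, not on the primary endpoint.

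**Working it through.** **Step 1: set the lists against the mechanism.**
- Safety outcomes (5.5): four. Clotting events among them: 0 of 4.
- Named risks (6.2): three. Clotting events among them: 0 of 3.
- Post-operative list (5.6): the one coagulation item is "prolong coagulation tests", which points towards bleeding.
- Exclusion criteria (5.7) and stopping criteria (5.6): no clotting event is named. A serious adverse event of any kind is a stopping criterion.
- Mechanism and exposure (5.5, 5.6): procoagulant, with medium to large vessels in the syringe group.

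**Step 2: ask what else could pick up a clot.**
- General adverse event recording could capture an evident event, but no definition or prompt is given.
- PT and PTT are drawn at baseline and at 24-48 hours and compared as means (7.2). A shortening could show, but a mean PT or PTT does not tell whether a vessel was occluded.
- ECG and radiology are in Table 1. After surgery their frequency is left to need, and neither is tied to a thrombotic outcome.

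**Step 3: look at the time window.** The last scheduled column ends at 48 hours, which is 2 days. Participation is 30 days, so 30 - 2 = 28 days have no scheduled column. A footnote carries the adverse event row past 48 hours when needed; the safety and physical examination rows carry no such mark.

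**Step 4: scale.** The core point has no figure of its own. The number of patients, 120, comes from sections 5.9 and 7.2 and reproduces. With 95% confidence, a margin of 5 points, a population of 175 and a proportion of 0.5 (assumed, not stated):
- n0 = z² × 0.25 / 0.05² = 384.15
- n = 384.15 / (1 + 383.15/175) = 120.4

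If clotting events were actively assessed in all 120 and none occurred, the exact one-sided 95% upper bound would be 1 - 0.05^(1/120) = 0.0247, or 2.5%. The two-sided 95% upper limit would be 1 - 0.025^(1/120) = 0.0303, or 3.0%.

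The chance of seeing at least one event is 1 - (1 - p)^120. The protocol gives no thrombosis rate, so p is assumed:
- p = 0.5%: 45%
- p = 1%: 70%
- p = 2%: 91%

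If only half of the events came to notice (also assumed), the effective rate halves. A true rate of 1% would then be seen with a chance of 45% instead of 70%, and a true rate of 2% with 70% instead of 91%. When the captured share is unknown, an absence of reports supports no bound.

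**The case against.** The best case for the protocol is that it has several nets. The post-operative list is expressly open-ended. Adverse events are a scheduled row in Table 1, next to a physical examination, and that row continues past 48 hours. The study form described in 7.1 is not shown, so what it prompts for is unknown. There is also a reason to watch for prolonged tests: section 5.5 reports that some bovine thrombin preparations are highly immunogenic, and 6.2 cites a hemophilia-like autoimmune reaction to sealants with Factor V, which SeraSeal does not contain. Finally, section 5.5 reports no adverse effects in two animal species at over 13,000 IU/kg, and in 5.6 excess product is removed.

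Much of this stands, and it rules out some tempting stronger readings:
- A reader might infer that coagulation is watched in one direction only. The documents do not support that: PT and PTT are measured from baseline and compared as means with no preset direction.
- A reader might infer that clotting would go wholly unassessed. That also goes too far, since an evident clot could be recorded as an adverse event.
- A reader might infer that admitting "Patients who are on anticoagulant therapy" makes the prolongation item worthless. A baseline draw is the ordinary way to handle such patients, nothing says that values would be flagged without regard to it, and baseline prolongation does not measure missed clots.
- A reader might infer that the product is known to cause thrombosis. No rate or signal is given; the hazard is an inference from the described mechanism.

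What the objection does not answer is that the stated basis of the safety determination leaves these events out, and that nothing shown defines or solicits them.

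**Conclusion.** The point holds as a gap in the named safety outcomes and risks. Thromboembolic events and occlusion of a treated vessel are absent from both lists, although the protocol describes a procoagulant product used where medium to large vessels may bleed. General adverse event recording softens the gap but does not close it, and no assessment column is scheduled in the last 28 of 30 days.

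The change should be made. It leaves the efficacy analysis untouched. The bound of 2.5% and the detection chances are for scale only. They assume that all 120 patients are exposed and assessed, and they use event rates that the protocol does not give. The conclusion needs none of them; it rests on the wording of sections 5.5, 5.6, 6.2, 8 and Table 1, and on the inference that excess clotting is a relevant hazard of activated clotting factors.

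**What to change.** **Main change.** Add thromboembolic events and occlusion of a treated vessel, each with a short definition, to the safety outcomes in section 5.5 and to the risks in section 6.2. Make them a solicited adverse event category on the existing study form. Ask about them at the physical examinations already in Table 1 and record them through the 30 days of participation. Use ECG and radiology results where these are already done; no added imaging is needed.

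**Secondary change.** Report PT and PTT as change from the patient's own baseline in both directions, with a descriptive split by anticoagulant use or blood disorder. The medical history and medication data for this are already collected. This does not replace recording clotting events.

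**Cost.** Protocol and form wording, one more solicited event category, and small subgroups in the PT and PTT tables. Table 1 shows no contact at day 30, so recording to that point needs a stated way of asking.
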